5. STUDY DESIGN

5.1 General Study Design

This is a Phase 1, multi-site, open label, nonrandomized, exploratory study to assess delivery of LMN-201 components via enteric capsules.

The trial will be evaluated through 2 cohorts of up to 6 subjects each. The first cohort will utilize specific components to allow analysis of individual component digestion. Eligible subjects with mature ileostomies will be consented, enrolled, assigned to treatment sequentially, and asked to swallow the following:

Subject	Number of capsules administered to subject—First cohort					
	Anti-toxin B VHH-1	Anti-toxin B VHH-2	Anti-toxin B VHH-3	Lysin capsules	Capsule with tube-shaped transit markers	Capsule with ring-shaped transit markers
1	3	—	—	1	1	1
2	3	—	—	1	1	1
3	—	3	—	1	1	1
4	—	3	—	1	1	1
5	—	—	3	1	1	1
6	—	—	3	1	1	1

Every hour after ingestion, ileostomy fluid will be collected, weighed, filtered, and analyzed for the presence of capsules and/or transit markers. This procedure will be repeated for four hours after the capsules and/or transit marker are observed in the ileostomy collection, or 12 hours after ingestion, whichever time is shorter.

The trial will be adapted between the first and the second cohort in the following manner:

- If intact enteric capsules are observed in the ileostomy fluid of more than one participant
 - And the transit time is less than 4 hours, then a fluid restriction to less than 150 ml per hour will be implemented for the second cohort.
 - And the transit time is greater than 4 hours, then immediate release capsules will be utilized for the second cohort.
- If the number of enteric capsules that remain encapsulated in the ileostomy fluid is less than 20%
 - Then the number of subjects in the second cohort will decrease to three.

The second cohort, allowing for the above changes, will utilize a ‘cocktail’ formulation of VHHS. Subjects will be asked to swallow the following:

Subject	Number of capsules administered to subject—Second cohort					
	Anti-toxin B VHH-1	Anti-toxin B VHH-2	Anti-toxin B VHH-3	Lysin capsules	Capsule with tube-shaped transit markers	Capsule with ring-shaped transit markers
1	1	1	1	1	1	1
2	1	1	1	1	1	1
3	1	1	1	1	1	1

Any changes not described above will only be implemented once a protocol amendment has been submitted to the appropriate Institutional Review Board (IRB) or Independent Ethics Committee (IEC), and has been reviewed and approved.

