8. STUDY EVALUATIONS

8.1 Specimen Preparation, Handling, and Shipping

Ileostomy fluid is collected prior to the administration of study capsules, filtered, and aliquoted (either unadulterated or supplemented with purified proteins and protease inhibitor to use as a positive control). Once study capsules are administered, ileostomy content is collected hourly for the duration of the protocol (up to 12 hours). Upon collection, they are filtered, and the retained material is examined for the presence of intact capsules, capsule remnants, and transit markers. If these are observed, a photograph is taken to record the findings. The pH and volume of the filtrate are measured and recorded. Five 10 mL aliquots are prepared, supplemented with a protease inhibitor, and immediately flash frozen and stored at -80 °C until shipment. For shipment, one positive control, half of the pre-treatment samples, and 1 tube from each timepoint are assembled and transported on dry ice to Lumen Bioscience at the end of the study.

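### As section 8.1 is written, no planned sample separates protein lost after the fluid leaves the stoma from the in vivo digestion that cohort 1 is meant to analyse (exploratory EIA endpoints only)

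*Protocol*

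**What the plan says.** Protocol section 8.1 describes the handling of post-dose fluid. It is collected every hour for up to 12 hours. Filtering and inspection follow: "Upon collection, they are filtered, and the retained material is examined for the presence of intact capsules, capsule remnants, and transit markers". A photograph is taken if anything is found. Next, "The pH and volume of the filtrate are measured and recorded". The inhibitor appears only after that: "Five 10 mL aliquots are prepared, supplemented with a protease inhibitor, and immediately flash frozen". The word for immediacy there governs the freezing, not the time from output to inhibitor. The section states no time limit, no cooling and no inhibitor in the collection vessel.

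Pre-dose fluid is filtered and aliquoted, "either unadulterated or supplemented with purified proteins and protease inhibitor to use as a positive control". The material shipped for assay is "one positive control, half of the pre-treatment samples, and 1 tube from each timepoint are assembled".

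Section 5.1 gives the purpose of the first cohort: "The first cohort will utilize specific components to allow analysis of individual component digestion". Section 4 makes EIA detection and EIA quantity exploratory endpoints, with between-subject variability in quantity as an exploratory objective. The primary endpoint is visual observation of capsules and transit markers.

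**The concern.** Section 3.1 regards digestion of the protein as the main obstacle to this product. Adding a protease inhibitor at all shows that proteolysis in the fluid is taken seriously. Yet the fluid is unprotected from the moment it leaves the stoma until it is aliquoted. Protein lost in that time reduces the EIA reading in the same direction as protein digested in the gut.

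A control could reveal this, but the one described cannot, because its inhibitor arrives with its protein. It would look normal whether the ex vivo loss was trivial or large.

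Two things are at stake. A low reading for one VHH or for lysin in cohort 1 would not show whether that component was digested in the gut or lost before freezing. In addition, differences between subjects in dwell time, handling time or protease activity would enter the variability that the second exploratory objective sets out to describe.

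**Working it through.** The protocol gives no figure on this point to reproduce. There is no hypothesis test and no sample size calculation (section 11.2). The check is a comparison of what each sample type goes through, followed by an illustration of size.

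**Step 1: follow the protein through each sample type described in section 8.1.**

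| Sample | Contains product protein? | Time without inhibitor | What it can show |
|---|---|---|---|
| Post-dose aliquots | Yes, if delivered | Output to aliquoting: up to about 60 min before collection, plus handling | Gut digestion and ex vivo loss combined |
| Positive control | Yes, purified protein added | None: protein and inhibitor added together | Assay recovery in the fluid; stability through freezing and shipping |
| Unadulterated pre-dose aliquots | No | Not applicable | Background signal |

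No row carries a known amount of protein through the unprotected interval, so ex vivo loss cannot be estimated from the described set.

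**Step 2: which steps precede the inhibitor.** Hourly collection and filtering must come first. In the listed order, pH and volume of the filtrate also come before aliquoting. Examination and photography concern the retained solids, not the filtrate, and can run alongside, so they are not counted as necessary delay.

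**Step 3: illustrate the size.** The documents give neither a half-life in ileal fluid nor a handling time; both are assumed here. With first-order decay and half-life *h* in minutes, *k* = ln 2 / *h*.

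- Fluid entering evenly over the hour: mean fraction left at collection = (1 − e^(−60*k*)) / (60*k*).
- Handling for *b* minutes: multiply by 2^(−*b*/*h*).

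Example for *h* = 60: (1 − 0.5) / 0.693 = 0.721. With *b* = 15, 0.721 × 2^(−0.25) = 0.721 × 0.841 = 0.607.

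| Assumed half-life (min) | At collection | Plus 15 min handling | Plus 30 min handling |
|---|---|---|---|
| 10 | 0.237 | 0.084 | 0.030 |
| 30 | 0.541 | 0.383 | 0.271 |
| 60 | 0.721 | 0.607 | 0.510 |
| 120 | 0.845 | 0.775 | 0.711 |
| 240 | 0.918 | 0.879 | 0.842 |

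**Step 4: effect on variability.** Take two subjects with equal true delivery, a 45-minute hold, and ex vivo half-lives of 30 and 120 minutes. The fractions left are 2^(−45/30) = 0.354 and 2^(−45/120) = 0.771, a ratio of 2.18. An apparent two-fold difference between subjects would then arise wholly outside the body.

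The loss may be minor or dominant, and the planned samples cannot show which.

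**The case against.** The strongest objection is that the operative procedure lies elsewhere. The Schedule of Activities and section 7.2 refer to a Manual of Procedures for fluid collection, and it is not shown. It may set chilling, a time limit or an extra control. That stands as a limit on what can be claimed about actual practice. It does not alter the control that section 8.1 itself describes, nor the point at which that section adds inhibitor.

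Second, the positive control is not defective for its ordinary purpose. An inhibited matrix spike properly checks recovery and stability in storage. That is right; it simply answers a different question from the one cohort 1 raises.

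Third, the dosed protein sits in whole spray-dried spirulina, so first-order decay of free protein may overstate the loss. That also stands and is one reason the table is only an illustration.

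A reader might also infer more than the text supports:

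- That the sponsor will read low EIA values as in vivo digestion. The protocol never says so. The endpoints concern protein in the collected fluid, and cohort 1 is said only to allow an analysis of digestion. The supportable claim is that the samples cannot separate the two.
- That the main result is at risk. The primary endpoint is visual, and no adaptation rule in section 5.1 uses the EIA.
- That inspection and photography hold up the inhibitor. They concern the retained material and need not delay the filtrate.
- That substantial degradation will occur. No figure in the documents shows this.

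**Conclusion.** The point holds in a limited form. As section 8.1 is written, post-dose fluid is without inhibitor from output until aliquoting, and the only protein-containing control is protected from the start. Ex vivo loss and in vivo component digestion therefore cannot be separated with the samples described.

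The consequence is confined to EIA detection, quantity and between-subject variability, all exploratory. Any such loss lowers values or produces false negatives. A positive detection remains valid, and a delivery claim based on one would be conservative.

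The size is unknown. The range of 0.38 to 0.88 remaining rests entirely on assumed half-lives of 30 to 240 minutes, 15 minutes of handling, even output over the hour and first-order decay; a 10-minute half-life would leave 0.08. The conclusion also assumes that the Manual of Procedures does not already add a hold-time control. The change is worth making because it is cheap and the fluid it needs is already being collected.

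**What to change.** 1. **Shorten the unprotected time.** As soon as the fluid is filtered, record the total filtrate volume, draw the EIA aliquots, add inhibitor and freeze. Examine and photograph the retained material in parallel and without delay, so that the primary observation is not postponed. Measure pH on the remaining filtrate. Volume must be recorded before the five 10 mL aliquots (50 mL in all) are removed, or output will be understated. Record the time from collection to inhibitor for every sample.

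2. **Add a hold-time control.** Reordering cannot remove the dwell before hourly collection, so this is the essential part. From the pre-dose fluid already collected, spike one aliquot per subject without inhibitor. Hold it for the collection-plus-processing interval under the same conditions, then inhibit and freeze it as a test sample. Compare it with the existing positive control to estimate ex vivo loss, and add it to the shipping list. Where feasible, spike with the spirulina biomass form, because purified protein may overstate the loss of biomass-borne protein.

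**Cost.** One extra tube and a few EIA wells per subject, for at most 12 subjects, with no further collection from them.

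**Limit.** The control gives an approximate bound, not an exact correction. Held for a full 75 minutes (60 + 15) at an assumed 60-minute half-life, it would retain 2^(−75/60) = 0.42, against a mean of 0.61 in fluid that entered evenly over the hour. Pre-dose fluid is also fasting fluid, whereas section 7.2 lets subjects eat from 2 hours after dosing, so protease activity may differ later in the day.

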9. INVESTIGATIONAL PRODUCT

9.1 Investigational Product (IP)

The investigational product (IP), individually encapsulated components of LMN-201, will be supplied by Lumen Bioscience. LMN-201 is being developed to be a cocktail consisting of a bacteriophage lysin specific for degrading the *C. difficile* organism and three VHH-derived proteins designed to bind and inhibit *C. difficile* toxin B, delivered in whole, spray-dried spirulina biomass.

The LMN-201 drug substance is manufactured using four stable cell lines engineered to express the respective lysin and VHHs. The substance is manufactured under Current Good Manufacturing Practices (cGMP) using recombinant DNA processes and controls. The cells are cultured using chemically defined, animal-product-free basal medium under photoautotrophic growth conditions, using bicarbonate and CO₂ as the carbon source. After harvesting and rinsing with a dilute solution of trehalose, cells are spray dried to produce drug substance. The drug substance is fully tested against established specifications prior to release for further processing and use in clinical studies. Each strain contains a single

prophylactic protein, and the prophylactic protein 'cocktails' are generated by growing these strains separately, spray drying them separately, and finally dry-mixing the resulting powders together.

The LMN-201 drug product is manufactured at Lumen Bioscience's cGMP manufacturing facility in Seattle, Washington, US. The individually encapsulated components of drug substance are provided in pre-formulated capsules. The individually encapsulated components of LMN-201 drug product are tested for potency and purity defined by established specifications. Lumen Bioscience's cell banking protocols are designed to comply with ICH guideline Q5D for microbial cells. LMN-201 drug products and the tube-shaped transit markers will be filled into Vcaps Enteric intrinsically enteric vegetarian capsules size 00 (Capsugel). Ring-shaped transit markers will be provided in manufacturers non-enteric capsules (Medifactia AB).

Transit markers (Transit-Pellets™ Radiopaque Markers, manufactured by Medifactia AB) will also be provided by Lumen Bioscience.

9.2 Dosing Regimen

Subjects will receive individually encapsulated components of LMN-201, taken as four (4) capsules (500 mg biomass in each capsule), orally. In addition, they will receive an immediate release capsule containing ring-shaped transit markers and an enteric capsule containing tube-shaped transit markers to allow calculation of transit time and encapsulation dissolution visually.

9.3 Dispensing of IP

The investigational team will dispense individually encapsulated components of LMN-201 and transit markers-containing capsules according to the study protocol.

9.4 Dosage Form

LMN-201 ingredients are spray-dried spirulina biomass and trehalose. Individually encapsulated components of LMN-201 doses (500 mg) are packaged in size 00, white, opaque capsules (Capsugel, Morristown, NJ, US), Vcaps Enteric (first cohort) and Vcaps Plus (second cohort, if adapted). Vcaps Enteric capsules incorporate pH-controlled release technology designed to release encapsulated components at or before the terminal ileum. Vcaps Plus capsules are immediate release capsules designed to release encapsulated components in the stomach. No capsules contain any materials of human or animal origin.

9.5 Route of Administration

Individually encapsulated components of LMN-201 and transit markers must be administered orally and will be taken with water only.

9.6 Timing of Dose

Capsules are to be self-administered by subjects upon confirmation of subject desire for participation.

9.7 Packaging and Labelling

The IP will be provided in a single dose packet with the appropriate labels.

9.8 Storage and Handling

All IPs will be kept in a locked area with limited access. Capsules containing IP should be stored at room temperature, 59-77°F (15-25°C) and protected from moisture, light, and extreme heat during storage.

Only subjects enrolled in the study may receive the IP in accordance with all applicable regulatory requirements. Upon the completion of the study, this material will be subjected to final inspection and reconciliation. At that time, all unused, partially used, and fully used (empty) container(s) along with a packing slip must be destroyed as per Pharmacy Manual. Documentation of destruction will be retained by the investigational pharmacy with the study files.

9.9 Study Intervention Compliance

A member of the study team will witness the ingestion of the IP.

10. SAFETY MANAGEMENT

10.1 Adverse Events (AEs)

The Principal Investigator (PI) is responsible documenting AEs according to the guidelines below.

An AE is any untoward medical occurrence or change in a clinical trial subject having received a biologic or medicinal product, whether or not considered treatment related. This may occur in any phase of the clinical study.

Events meeting the AE definition include:

- Any noxious, pathological, or unintended change in anatomical, physiologic, or metabolic functions as indicated by physical signs, symptoms, and/or clinically significant laboratory abnormalities
- Exacerbation or worsening of pre-existing conditions or events
- Intercurrent illnesses, injuries, or vaccine or drug interaction
- Worsening of abnormal clinical laboratory values

Stable, pre-existing conditions and/or elective procedures are not AEs.

10.2 Documenting and Reporting AEs

All observed or volunteered AEs regardless of suspected causal relationship to the IP will be recorded on the AE page(s) of the case report form (CRF). The investigator must assess all AEs for seriousness, severity, and relation to IP.

The PI will follow all AEs, regardless of seriousness or severity, until the event or its sequelae resolve or stabilize at a level acceptable to the investigator.

The investigator is responsible for ensuring appropriate clinical management of all AEs until they are resolved or stabilized at a level acceptable to the investigator. Appropriate clinical management of AEs is at the discretion of the investigator.

10.3 Expedited Recording of Serious Adverse Events (SAEs)

Any SAE must be reported to the Sponsor within 24 hours.

Instructions:

The following information should be sent via email (preferred) or telephone:

- *Protocol IND number, IP, PI name, and contact number*
- *Subject identification number*
- *Serious adverse event (SAE), onset date, date of IP administration, severity, relationship, and subject's status*

AND email the following documents to Medical Monitor, Lumen Bioscience:

- *Cover sheet*
- *Adverse Event (AE) CRF*
- *Supplemental SAE Report Form*
- *Concomitant Medication CRF or a list of concomitant medications*
- *Medical record progress notes including pertinent laboratory/diagnostic test results*

The PI will assess all SAEs as being either related or unrelated to the administered product.

Investigators are required to forward safety information provided by the Sponsor's representative to the IRB/IEC. All SAEs will be reported to the IRB/IEC within 24 hours of the PI becoming aware of the event:

Bellberry Limited HREC
 [name]
 [name]
 [contact]
 Email: [contact]

11. STATISTICAL CONSIDERATIONS

11.1 Introduction

Safety, clinical outcomes, and outcome data will be entered into the data system. Data will be edited with standard strategies for range and consistency checks. AEs for all subjects will be included in the safety analysis.

11.2 Sample Size Considerations

No statistical hypothesis is required to be tested. Therefore, no formal sample size calculations have been made. The sample size has been determined to be up to six (6) per cohort to provide preliminary information.

Overall, up to 12 human subjects will be exposed to the IP.

11.3 Safety

Preliminary analysis of safety and tolerability will include all subjects who received study drug. Safety will be evaluated from reported AEs, physical examination findings, and vital signs.

12. DATA HANDLING AND RECORD KEEPING

The PI will maintain complete and accurate documentation for the study. All required study data will be clearly and accurately recorded by authorized study personnel in the electronic CRFs (eCRFs). Only designated study site personnel shall record or change data in an eCRF. The PI will be responsible for the procurement of data and for quality of data recorded in the eCRFs. Original observations entered directly into the eCRFs are considered source data. Study-specific procedures detail how each form will be completed. The study coordinator will ensure accuracy of the CRFs. All source documents will be retained at the site.

A detailed data management plan will be written and approved by the study team and the PI. The plan will be drafted prior to study initiation but will be finalized before study close-out and database lock.

13. CLINICAL TRIAL MATERIAL ACCOUNTABILITY

The site PI is responsible for maintaining accurate records of the processing and use of all clinical trial materials. All used, unused, or undispensed study medication must be accounted for by the site PI.

Drug accountability will be conducted during monitoring visits to ensure appropriate receipt, storage, dispensing, and documentation of returned Clinical Trial Materials.

14. QUALITY CONTROL (QC)/QUALITY ASSURANCE (QA)

14.1 QC/QA Monitoring

During the study and at the close-out, a monitor from Lumen Bioscience or its representative will have regular contacts with the investigational site for the following:

- Provide information and support to the Investigator(s)
- Confirm that facilities remain acceptable
- Confirm that the investigational team is adhering to the protocol, data is being accurately recorded in the CRFs, and IP accountability checks are being performed
- Perform source data verification. This includes a comparison of the data in the CRFs with the subject's medical records at the hospital or practice, and other records relevant to the study. This will require direct access to all original records for each subject (e.g., clinic charts)
- Record and report any protocol deviations not previously sent to Lumen Bioscience
- Confirm AEs and SAEs have been properly documented on CRFs and confirm any SAEs have been forwarded to Lumen Bioscience or its representative and those SAEs that met criteria for reporting have been forwarded to the IRB/IEC and/or FDA

The monitor will be available between visits if the Investigator(s) or other staff needs information or advice. The PI assumes ultimate responsibility for the conduct of the study and remains readily accessible throughout the duration of the study.

14.2 Audits and Inspections

Authorized representatives of Lumen Bioscience or a regulatory authority may visit the site to perform audits or inspections, including source data verification. The purpose of a Lumen Bioscience audit or inspection is to systematically and independently examine all study-related activities and documents to determine whether these activities were conducted, and data were recorded, analyzed, and accurately

reported according to the protocol, Good Clinical Practice (GCP) guidelines of the International Conference on Harmonization, and any applicable regulatory requirements. The Investigator should contact Lumen Bioscience immediately if contacted by a regulatory agency about an inspection.

The Investigator agrees to allow the monitor to inspect the drug storage area, study drug stocks, drug accountability records, subject charts and study source documents, and other records relative to study conduct.

To ensure compliance with GCP and all applicable regulatory requirements, Lumen Bioscience may conduct one or more quality assurance audits.

